3.2. Sample Size Determination

The total sample size required is 48 subjects (16:16:8:8) (high-dose ADP101: low-dose ADP101: high-dose placebo: low-dose placebo) for the study. Assuming a 20% pediatric subject dropout rate based on the dropout rate observed in prior oral immunotherapy (OIT) studies, a total of 60 pediatric subjects will be randomized 2:2:1:1 into the 4 arms. The planned randomization scheme is anticipated to enable completion through Week 40 for 16 subjects in each active dose regimen, and a total of 16 subjects taking placebo (8 per placebo dose regimen).

The adequacy of the sample size was confirmed by performing simulations for power calculations using the Fisher's exact test for each of 2 doses (vs. placebo) under alternative hypotheses. Assuming placebo response rates of 4% and active response rates of 40% and 58% in the low- and high-dose regimen treatment groups, respectively (based on [\(Vickery, 2018\)](#)), and an alpha of 5%, power was calculated using the Simes global test ([Simes, 1986](#)) with the Holm procedure ([Holm, 1979](#)) to reject at least 1 of the doses. Results showed approximately 90% power to detect a statistically significant ADP101 response in at least 1 of the doses with the given sample size.

Additionally, a total of approximately 12 adult subjects will be randomized to the 2 doses of ADP101 (approximately 4 subjects on each of the high- and low-dose regimens and 4 subjects on placebo), to provide an initial exploration of the safety and efficacy in this population, as well as the feasibility of enrolling adult subjects in subsequent studies with ADP101. Thus, a total of approximately 72 subjects will be enrolled in this study.

The sample size for the study is sufficient to test the superiority of ADP101 over placebo for pediatric subjects aged ≥ 4 to < 18 years who tolerate at least 600 mg on the Exit DBPCFC of a single qualifying food source within ADP101 without dose-limiting symptoms after 40 weeks of treatment (primary efficacy endpoint) with at least 1 of the 2 dosing regimens (low/1500 mg or high/4500 mg).

A claim of statistical significance will be not be made for the primary endpoint unless the superiority of ADP101 over placebo is demonstrated in at least 1 of the 2 doses (treatment groups).

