- All tests of treatment effect will be conducted at a 2-sided alpha level of 0.05, unless otherwise stated. Any confidence intervals (CIs) of the statistical models will be rounded to 1 decimal place. All model estimates, such as least-squares (LS) means if applicable, will be rounded to 2 decimal places. Any calculated p-values will be rounded to 3 decimal places; p-values less than 0.001 will be presented as 'p < 0.001' and p-values greater than 0.999 will be presented as 'p > 0.999'.
- Multiple assessments at a given time point (planned, repeat, and unscheduled) will not be included in summary tables unless specified otherwise, but will be included in the listings. All assessments will be used in analysis of maximum changes or shift analyses.

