7.8.1. Primary Efficacy Endpoint and Analysis

The primary endpoint is a ≥ 600 mg desensitization response as determined by tolerating ≥ 600 mg of food protein at the Exit DBPCFC without dose-limiting symptoms for at least 1 qualifying food.

Any subject who does not meet this definition will be considered a non-responder.

Classification as a 1000 mg responder is defined similarly.

Primary Analysis

The primary analysis of the primary endpoint will be performed on pediatric subjects in the ITT Population by treatment group.

The number and percent of subjects with a ≥ 600 mg desensitization response will be reported by treatment group. The primary endpoint hypothesis of superiority of ADP101 over pooled placebo will be tested using the Fisher's exact test. The unadjusted p-values will be reported. The difference in the proportions of responders (ADP101 vs. pooled placebo) with Newcombe 95% CIs will be reported using PROC FREQ procedure in SAS® and the RISKDIFF option.

A sample SAS code for the proc freq is provided below:

Ods output PdiffCL=pdiff

Proc freq

```
data=indata;  
TABLE trtgrp*endpoint/ chisq riskdiff(cl=( newcombe ) correct );  
OUTPUT out=outdata CHISQ RDIF1 ;
```

RUN;

In order to handle the comparison of multiple active groups versus pooled placebo, the overall type-I error will be controlled by the use of the Simes global test (Simes, 1986) with the Holm procedure (Holm, 1979) to adjust for and test the global (joint) hypothesis that at least one of the 2 hypotheses below is rejected.

- H_{01} : proportion of responders in pooled placebo group = proportion of responders in low-dose (1500 mg) group
- H_{02} : proportion of responders in pooled placebo group = proportion of responders in high-dose (4500 mg) group.

The adjustment for multiplicity for the joint hypothesis in support of the primary efficacy endpoint will be performed using the PROC MULTTEST procedure in SAS® (HOLM option). The adjusted p-values will be reported along with the unadjusted p-values described above.

All efficacy-related data will be listed. Tables for the primary efficacy endpoint will include proportion of responders who tolerated at least 600 mg in pooled placebo vs low dose group and pooled placebo vs high dose group in ITT. The unadjusted and adjusted p-values will be displayed.

Sensitivity Analysis

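### Fisher's exact test with Holm is valid but spends only about half of the allowed 5% familywise error when groups are equal; Boschloo's exact test would add power cheaply, by an amount that depends on the final group sizes

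*SAP*

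**What the plan says.** The primary analysis in SAP 7.8.1 compares each dose with pooled placebo in pediatric ITT subjects: "The primary endpoint hypothesis of superiority of ADP101 over pooled placebo will be tested using the" Fisher's exact test. For the two dose hypotheses, "the overall type-I error will be controlled by the use of the Simes global test (Simes, 1986) with the Holm procedure", and the adjustment "will be performed using the PROC MULTTEST procedure in SAS® (HOLM option"). SAP 6.1 sets the level: "All tests of treatment effect will be conducted at a 2-sided alpha level of 0.05, unless otherwise stated". SAP 7.8.2 carries the same method to the secondary endpoints but displays only the Fisher p-values.

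SAP 3.2 gives the power basis: "Assuming placebo response rates of 4% and active response rates of 40% and 58% in the low- and high-dose regimen treatment groups, respectively". It also says "The total sample size required is 48 subjects (16:16:8:8"), which makes 16 in the pooled placebo group, and concludes: "Results showed approximately 90% power to detect a statistically significant ADP101 response in at least 1 of the doses". Sixty children are randomized to allow for 20% dropout. Protocol 9.4.3 counts subjects who drop out or stop study drug before the Exit food challenge as failures. Neither document states the type I error actually attained or considers an unconditional exact test.

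**The concern.** Fisher's test conditions on the total number of responders. With about 20 children per group and a placebo rate near 4%, few distinct p-values are possible, and the rejection region can fall well short of the allowed level. The unused error rate costs power.

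Boschloo's test takes the Fisher p-value as its statistic and computes the exact worst-case probability of a value that small over the unknown common response rate. Its p-value cannot exceed Fisher's, and its size cannot exceed the nominal level. At stake is power from the same children under the same error limit, including for the low dose, which is the weaker comparison and matters because Protocol 4.2 says the study will help to assess the optimal dose.

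**Working it through.** **Inputs.** Two-sided 0.05 (SAP 6.1). Holm over two comparisons (SAP 7.8.1). Placebo pooled (SAP 6.6). Rates 4/40/58% and 16 per group for power (SAP 3.2). Sixty children randomized 2:2:1:1, so 20/20/20 after pooling. Protocol 2.3.2 reports 61 children randomized.

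**Method.** Exact enumeration of the three binomials (low, high, shared placebo). Holm rejects at least one hypothesis when the smaller p-value is at most 0.025. For placebo count c, let A_L(c) and A_H(c) be the probabilities that the low-dose and high-dose p-values are at most 0.025, and B_L(c) the probability that the low-dose p-value is at most 0.05. Then:
- any-dose power = Σ_c P(c) × [1 − (1 − A_L(c)) × (1 − A_H(c))]
- low-dose power = Σ_c P(c) × [A_L(c) + (B_L(c) − A_L(c)) × A_H(c)]

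The familywise error is the first sum with all three rates equal, maximized over the common rate. Boschloo p-values order the tables by two-sided Fisher p-value and maximize over the common rate.

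**Step 1: the plan's own figure.** With 16/16/16 and 4/40/58%, Fisher with Holm gives 89.99% (90.9% if Simes is used for the global test). This reproduces the stated figure of about 90%. Separate placebo arms of 8 would give only 70%, so the stated figure uses pooled placebo. Also 48 / 0.80 = 60.

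**Step 2: attained error.** Fisher with Holm has a maximum familywise error of 1.94% at 16 per group and 2.61% at 20 per group (Simes 2.00% and 2.66%). Boschloo with Holm has 3.8% and 4.2%, and at most 4.6% when one dose works and the other does not.

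**Step 3: where the gap comes from.** Take 5/20 against 0/20. The two tails are equal, so Fisher p = 2 × C(20,5)/C(40,5) = 2 × 15,504/658,008 = 0.0471. Boschloo gives 0.0225. For 7/20 against 1/20 the values are 0.0436 and 0.0215. Both tables pass Holm's first threshold of 0.025 only under Boschloo. With one more placebo child, 5/20 against 0/21, the opposite tail, C(21,5) = 20,349, exceeds 15,504 and is not counted. Fisher p is then 15,504/749,398 = 0.0207, which already passes.

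**Step 4: power at the SAP's rates, Fisher to Boschloo.**
- 16 per group: any dose 90.0% to 94.0% (+4.0)
- 20 per group: any dose 96.3% to 98.4% (+2.1); low dose 75.7% to 83.8% (+8.1)

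**Step 5: diluted rates (an assumption).** If 4/40/58% are completer rates and 20% drop out as failures, the ITT rates are 0.8 × 4 = 3.2%, 0.8 × 40 = 32% and 0.8 × 58 = 46.4%. With 20 per group, any-dose power goes from 86.8% to 93.2% (+6.4), or from 83.3% to 90.9% (+7.6) if placebo stays at 4%.

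**Step 6: group sizes.** Fisher / Boschloo; sizes are low/high/placebo; diluted means 32/46.4/3.2%.

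| Sizes | Max. familywise error | Any dose, SAP rates | Any dose, diluted |
|---|---|---|---|
| 20/20/20 | 2.6% / 4.2% | 96.3% / 98.4% | 86.8% / 93.2% |
| 21/20/20 | 2.9% / 3.8% | 96.6% / 98.2% | 87.5% / 92.5% |
| 20/21/20 | 2.9% / 3.8% | 97.4% / 97.9% | 89.3% / 91.0% |
| 20/20/21 | 3.3% / 3.9% | 98.3% / 98.4% | 92.8% / 92.8% |
| 21/21/19 | 3.0% / 4.3% | 97.7% / 98.5% | 90.4% / 92.2% |
| 19/21/21 | 2.7% / 4.2% | 97.4% / 98.8% | 89.8% / 94.3% |

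Over all the 61-child splits tried, Fisher's maximum error is 2.7% to 3.3%. The any-dose gain is 0.0 to 1.6 points at the SAP rates and 0.0 to 4.9 points with all rates diluted (up to 5.9 if placebo stays at 4%).

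**The case against.** The strongest defense is that nothing in the plan is wrong. Fisher's test with Holm controls the error, and SAP 3.2 computed power with that test, so its conservatism is already inside the 90%. This stands. Preferring an unconditional exact test is a question of efficiency.

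A reader might infer that the plan throws away 6 or more points of any-dose power, or that its real power is below 90%. The documents do not support either. At their own rates the any-dose loss is 2.1 to 4.0 points with equal groups, and Fisher already gives 96.3% with all 60 children. The larger figures need the 20% dilution. Inflating 48 to 60 for dropout suggests completer rates. However, Protocol 4.3 reports 62% to 67% of children passing 600 mg in earlier peanut trials, in a sentence that refers to an ITT analysis, and the assumed 58% lies below that. The documents never say which kind of rate was meant.

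The group sizes also matter. Sixty-one children cannot form three equal groups, and at 20/20/21 the gain disappears. Nor does the low dose always gain most: at 21/20/20 with diluted rates its gain is only 1.1 points. The same sensitivity counts against Fisher's test, though: one extra placebo child moves its diluted power from 86.8% to 92.8%, while Boschloo stays at or above 91% in every split in the table.

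Timing is the most serious practical objection. SAP 3.4 unblinds subjects on a rolling basis after their own data are locked. Protocol 2.3.2 reports at least 159 days of exposure by 2 March 2022. If that is every child's minimum, Week 40 (280 days) falls 121 days later, about 1 July 2022. Adding 8 weeks of challenges and 4 weeks to End of Treatment gives late September. SAP 2.0 is dated 19 October 2022. Protocol 9.4 bars study personnel from aggregating unblinded data before database lock, but the documents do not show who had seen individual outcomes by arm.

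**Conclusion.** This is a cheap efficiency improvement to a valid analysis. With equal groups, Fisher with Holm uses 1.9% to 2.6% of the allowed 5%. Boschloo with Holm keeps every Fisher rejection and stays below 5%. The firmest gains, which need no assumption beyond the SAP's rates and equal groups, are those in Step 4: 2 to 4 points for any dose, and about 8 points for the low dose at 20 per group. The 6.4 to 7.6 points in Step 5 depend on reading the design rates as completer rates. With 61 children the any-dose gain may be anything from nil to about 2 points at the design rates, or to about 5 at the diluted rates. The stated 90% power is correct for the plan as written.

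**What to change.** In SAP 7.8.1 and 7.8.2, name Boschloo's two-sided exact unconditional test for each dose against pooled placebo. Apply Holm to the resulting p-values for the primary endpoint, and report Fisher's test as a sensitivity analysis. Specify that tables are ordered by the two-sided Fisher p-value and that the maximum is taken over the common response rate; the property of keeping every Fisher rejection belongs to that definition. Restate power for this test at the final group sizes, and say whether 40% and 58% are completer or ITT rates.

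Make the change only if it is documented before any outcomes by arm are known. If that cannot be shown, keep Fisher as primary and report Boschloo as supportive.

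The cost is SAP wording and a standard exact routine. The downside is a less familiar test that does not condition on the total number of responders.

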9.4.3. Efficacy Analyses

For lists of objectives and endpoints, refer to Section 3.

Since the superiority of ADP101 at different doses over placebo will be tested, the primary and secondary efficacy analyses will be based on the ITT Population. The primary, secondary, and exploratory efficacy analyses will be performed on the ITT Population, as well as the PP Population (based on the ITT principle). Sensitivity analyses, to be described in full in the SAP, will be performed on subsets of the PP Population, e.g., including or excluding subjects who discontinue study drug prematurely due to treatment-related or unrelated reasons. For efficacy analyses, subjects will be analyzed according to randomized treatment.

Primary and secondary efficacy endpoints will be analyzed using Simes' Test with the Holms procedure (multiple p values will be elaborated in the SAP) and Fisher's exact test for dose selection. All individuals failing to achieve the success in the endpoint definition described above in Section 3 will be considered treatment failures. All individuals who drop out of the study or discontinue study drug prior to undergoing the Exit DBPCFC will be considered treatment failures (i.e., Missing = Failure).

Exploratory efficacy endpoints will be analyzed using descriptive statistics. Details will be included in SAP for the study.

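### SAP 7.8.1 pairs the Simes global test with Holm but codes only Holm and does not say which governs: a minor inconsistency with a small power cost

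*SAP*

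**What the plan says.** SAP 7.8.1 tests each dose against pooled placebo with Fisher's exact test. For the joint hypothesis over the two doses it says that "the overall type-I error will be controlled by the use of the Simes global test (Simes, 1986) with the Holm procedure (Holm, 1979"). It then specifies PROC MULTTEST with the HOLM option and adds: "The adjusted p-values will be reported along with the unadjusted p-values described above." No Simes global p-value is listed as an output.

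The pairing recurs elsewhere. SAP 3.2 (and protocol 9.2) describes the sample size with "an alpha of 5%, power was calculated using the Simes global test" together with Holm. Protocol 9.4.3 says: "Primary and secondary efficacy endpoints will be analyzed using Simes' Test with the Holms procedure," and leaves the detail to the SAP.

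The rule for claiming success is in SAP 3.2 and protocol 9.1. No claim of significance is made on the primary endpoint unless at least one of the two doses is shown superior to placebo. Protocol 9.4 lets the SAP prevail where the two documents diverge.

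**The concern.** Simes and Holm are not a matched pair. Simes tests the joint null that neither dose works. The dose-level procedure obtained by closing it is Hochberg's, which for two hypotheses is identical to Hommel's. Holm is the closure of the Bonferroni test, which is stricter. A plan that names Simes for the joint hypothesis and Holm for the doses can therefore reject the joint null and no dose.

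If that happened, a reader could point to the Simes result as evidence that at least one dose works, while the adjusted p-values in the table said otherwise. The tipping-point analysis in SAP 7.8.1 starts only if the primary analysis is statistically significant, so the same uncertainty would carry into it. Holm also gives up a little power compared with the procedure that matches Simes.

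**Working it through.** **Inputs**

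- Family-wise alpha 5% (SAP 3.2), two-sided: "All tests of treatment effect will be conducted at a 2-sided alpha level of 0.05, unless otherwise stated" (SAP 6.1).
- Rates: "Assuming placebo response rates of 4% and active response rates of 40% and 58% in the low- and high-dose regimen treatment groups" (SAP 3.2).
- Completers: "The total sample size required is 48 subjects (16:16:8:8") (SAP 3.2), so 16 per dose and 8 + 8 = 16 pooled placebo.
- Randomized: "Assuming a 20% pediatric subject dropout rate based on the dropout rate observed in prior oral immunotherapy (OIT) studies" (SAP 3.2) gives 48 / 0.8 = 60 pediatric subjects, that is 20 per dose and 10 + 10 = 20 pooled placebo.
- Comparator: pooled placebo (SAP 6.6). Test: Fisher's exact (SAP 7.8.1).

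**Decision rules.** Let p(1) ≤ p(2) be the two dose p-values.

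- Simes global p = min{2·p(1), p(2)}. It rejects the joint null if p(1) ≤ 0.025 or p(2) ≤ 0.05.
- Holm-adjusted p-values: 2·p(1), and max{2·p(1), p(2)}. At least one dose is rejected only if p(1) ≤ 0.025.
- Hochberg-adjusted p-values: min{2·p(1), p(2)}, and p(2). The smaller one equals the Simes p, so global and dose-level results always agree.

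Simes rejects and Holm does not exactly when p(1) > 0.025 and p(2) ≤ 0.05, so both p-values lie in (0.025, 0.05]. The power gained by moving from Holm to Hochberg is the probability of that event.

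**The plan's own figure.** Exact binomial enumeration with 16/16/16 subjects and rates 4%/40%/58% gives 89.99% power to reject at least one dose under Holm and 90.86% under Simes/Hochberg. Both match the stated approximate 90%. (This reproduces against pooled placebo. Protocol 9.2's wording of 16 versus 8 same-dose placebo gives about 70% two-sided, which is a separate matter.)

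**Where the methods disagree.** With 20 per group and placebo counts of 0 to 5, the window is reached only at placebo/low/high responder counts 0/5/5, 1/7/7, 2/9/9, 3/10/10 and 4/11/11. Higher placebo counts contribute nothing visible at a 4% placebo rate.

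Example, 0/20 against 5/20 in both doses: Fisher p = 2 × C(20,5) / C(40,5) = 2 × 15504 / 658008 = 0.0471 for each dose. Simes global p = min(0.0942, 0.0471) = 0.0471, so it rejects. The Holm-adjusted p is 0.094 for each dose, so neither is rejected. At the planning rates this particular outcome has probability about 0.007%.

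**Power to reject at least one dose**

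| Scenario (placebo/low/high) | Holm | Hochberg | Gain (points) |
|---|---|---|---|
| 16 per group, 4/40/58% | 89.99% | 90.86% | 0.9 |
| 20 per group, 4/40/58% | 96.28% | 96.70% | 0.4 |
| 20 per group, all rates × 0.8 (assumption) | 86.82% | 87.90% | 1.1 |
| 20 per group, active rates only × 0.8 (assumption) | 83.33% | 84.48% | 1.2 |
| 20 per group, 4/30/30% (assumption) | 52.90% | 55.37% | 2.5 |

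The two × 0.8 rows treat the 20% dropouts as failures and the stated rates as completer rates. The documents do not say that the rates were meant that way.

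**Error control, 20 per group.** With equal rates in all three groups, scanned across the range of rates, the probability of rejecting at least one dose is at most 0.027 under either method. If only one dose is null, rejecting it needs its own Fisher p ≤ 0.05, and the exact size of that single test is at most 0.026. Both figures are well below 0.05.

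**The case against.** The strongest reply is that nothing in the decision is open. The sentence in SAP 7.8.1 names Holm as well as Simes, so the HOLM option carries out a named procedure. The claim rule is at dose level, and Simes identifies no dose. The planned tables show Holm-adjusted p-values and no Simes p-value, so 0/5/5 would yield 0.094 twice and no claim. Holm needs no assumption about dependence, and it meets the planned power unaided.

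All of this stands, and it rules out three stronger readings. A reader might infer that the code departs from the text; it does not, because the text names both methods. A reader might infer that the success criterion is left undecided; the dose-level rule together with the coded output settles it. A reader might infer that type I error or the planned power is compromised; the enumeration shows neither.

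What the reply leaves standing is narrower. The plan gives Simes responsibility for error control on the joint hypothesis and then gives it no step and no output. No sentence says that Holm governs; the reader has to work that out by combining two sections.

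**Conclusion.** The inconsistency is real and minor. Simes is named, only Holm is coded, and no governing rule is stated. Under the planning assumptions the two methods would disagree in 0.4% of trials (20 per group) to 0.9% (16 per group), and the same figures in percentage points are the power lost by using Holm. The loss is 1.1 to 1.2 points if 20% dilution is assumed and about 2.5 points if both doses respond at 30% against 4% on placebo; those last two cases rest on assumptions that are not in the documents. Any conflict would be one of reporting, since the coded Holm result would decide the claim. The case for acting is that clarification is cheap and that two named methods with no stated priority leave room for argument after unblinding.

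**What to change.** Before database lock, replace HOLM with HOCHBERG in PROC MULTTEST (HOMMEL gives the same result for two tests). State in SAP 7.8.1 that this is the sole procedure governing the at-least-one-dose claim, and make SAP 3.2 and protocol 9.2 and 9.4.3 agree. Hochberg never rejects less than Holm, and its global and dose-level decisions cannot conflict.

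The cost is one code option and edits in four places. The statistical price is reliance on positive dependence between the two tests. The shared pooled placebo group makes that plausible, and the exact family-wise error of at most 0.027 leaves ample room. SAP 3.4 unblinds subjects on a rolling basis, so a move to the less strict procedure should be dated and made without sight of unblinded efficacy data.

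If the sponsor prefers Holm, delete the Simes references and state that Holm alone governs. That cures the ambiguity with no change to the code and forgoes only the small power gain.

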In addition to the analyses described above, the following supportive analyses will be performed using the primary endpoint:

- The Farrington-Manning non-inferiority test will be used to compare the primary endpoint response rates of high-dose ADP101 vs. pooled placebo and low-dose ADP101 vs. pooled placebo using a margin of inferiority of 15%.
- The comparison of the primary endpoint between the pooled ADP101 vs. pooled ADP101 will be provided using the Fisher's exact test.
- The analysis of the primary endpoint will be performed for 2 additional populations, 1) all subjects (pediatric and adult subjects combined) and 2) adult subjects in the ITT Population. The same method as described in the primary analysis above (for pediatric subjects) will be used for all subjects and the unadjusted p-values will be reported. Descriptive statistics corresponding to the primary endpoint response rates will be reported for adult subjects.

The plots of subjects with a ≥ 600 mg desensitization response will be provided for pediatric, adult and all subjects in the ITT population and pediatric subjects in the PP population.

Subgroup Analysis

Subgroups of ITT subjects who reached their target dose as their maintenance dose (see Section 6.7) will be analyzed for the primary endpoint. The subjects with ≥ 600 mg desensitization response by reached target dose will be plotted for pediatric subjects in the ITT population.

The 15 ADP101 individual foods will be consolidated into 9 foods/food groups, including peanut, tree nuts (almond, cashew, hazelnut, pecan, pistachio, or walnut), milk, egg, soy, wheat, shrimp, finfish (codfish or salmon), and sesame. Descriptive statistics, such as response rate differences and corresponding 95% CIs, will be provided for each ADP-101 food/food group above as long as there is sufficient sample size in that food/food group. The response rate for each food/food group will be based on the number of subjects with qualifying food allergies within the category.

Supplemental Analyses using the Estimand Framework

The primary and top secondary endpoint will be analyzed using the Estimand framework outlined in the E9(R1) (Statistical Principles for Clinical Trials: Addendum: Estimands and Sensitivity Analysis in Clinical Trials) guidance. The intercurrent event of interest is study discontinuation without completing the exit DBPCFC for any of the subject's qualifying food allergies.

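### SAP 7.8.1 plans a supportive test of non-inferiority to placebo with a 15% margin; a pass rules out only a 15-point deficit and cannot support superiority

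*SAP*

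**What the plan says.** The primary analysis in SAP Section 7.8.1 is a superiority comparison: "The primary endpoint hypothesis of superiority of ADP101 over pooled placebo will be tested using the Fisher's exact test", with Simes/Holm control over the two doses. An effect estimate goes with it: "The difference in the proportions of responders (ADP101 vs. pooled placebo) with Newcombe 95% CIs will be reported". SAP Section 3.2 and Protocol Section 9.1 allow no claim of significance on the primary endpoint "unless the superiority of ADP101 over placebo is demonstrated in at least 1 of the 2 doses".

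Further down Section 7.8.1, under Supportive Analyses, the text announces that "the following supportive analyses will be performed using the primary endpoint". The first item is: "The Farrington-Manning non-inferiority test will be used to compare the primary endpoint response rates of high-dose ADP101 vs. pooled placebo", and also "low-dose ADP101 vs. pooled placebo using a margin of inferiority of 15" percent.

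The bullet gives no null hypothesis, no scale for the margin, no level or sidedness of its own, no reason for 15%, and no account of what a pass would mean. The efficacy section of the protocol (9.4.3) contains no non-inferiority test, and SAP Section 9, which lists changes from the protocol, does not mention one.

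**The concern.** Non-inferiority testing suits a comparison in which being about as good as the comparator is a useful result. Against placebo it is not: a product that merely matches placebo has failed. This test can be passed by a product with no effect, or by one somewhat worse than placebo.

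What is at stake is the reading of the results. Each dose would carry an extra p-value, labelled supportive of the primary endpoint, that can fall below its threshold when the Fisher test shows nothing. It would mislead most in the trial where the primary analysis fails and a significant-looking supportive result stands next to it.

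**Working it through.** **Inputs**
- Placebo 4%, low dose 40%, high dose 58% (SAP 3.2: "Assuming placebo response rates of 4% and active response rates of 40% and 58" percent).
- Pediatric subjects randomized 20:20:10:10, so 20 per dose against 20 on pooled placebo (SAP Table 1 and Section 6.6). Planned completers 16:16:8:8, so 16 against 16 (SAP 3.2).
- Margin 15%, taken as percentage points on the risk difference. This is an assumption; the SAP gives no scale.
- Level: SAP 6.1 sets "All tests of treatment effect will be conducted at a 2-sided alpha level of 0.05, unless otherwise stated". I take one-sided 0.025 from this and also show one-sided 0.05.
- Population: pediatric, as in the primary analysis. The bullet names none.

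**The plan's own figure.** Exact enumeration of two-sided Fisher tests, each dose (n = 16) against the shared pooled placebo (n = 16), gives power to reject for at least one dose of 0.900 with Holm and 0.909 with Simes. The stated 90% reproduces. No power is stated for the non-inferiority test.

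**The hypothesis tested.** H0: p(ADP101) − p(placebo) ≤ −0.15. If p(placebo) = 0.04, H0 requires p(ADP101) ≤ 0.04 − 0.15 = −0.11, which is impossible. The same holds for any placebo rate below 15%. At 15% or above H0 is possible, but rejecting it still says nothing about a benefit.

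**The statistic.** z = (x1/n1 − x2/n2 + 0.15) / SE, where SE = √[r1(1−r1)/n1 + r2(1−r2)/n2] and r1, r2 are the maximum likelihood rates under the constraint r2 = r1 + 0.15. The dose passes if z > 1.96.
- 1/20 vs 0/20: r1 = 0.023, r2 = 0.173, SE = 0.0909, z = 0.20/0.0909 = 2.20, one-sided p = 0.014. Pass. Fisher p = 1.0. The Newcombe 95% CI is about −12 to +24 points, or −16 to +27 with the continuity correction in the SAP's sample code.
- 0/20 vs 0/20: SE = 0.0798, z = 0.15/0.0798 = 1.88, p = 0.030. No pass.

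**Responders needed on ADP101 (20 vs 20)**

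| Placebo responders | To pass non-inferiority | For two-sided Fisher ≤ 0.05 |
|---|---|---|
| 0 | 1 | 5 |
| 1 | 3 | 7 |
| 2 | 4 | 9 |

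**Pass probability for a given dose**, by enumerating all outcomes (20 vs 20, one-sided 0.025; the Fisher column is two-sided 0.05, unadjusted, in favour of ADP101)

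| ADP101 vs placebo | Non-inferiority passes | Fisher favours ADP101 |
|---|---|---|
| 2% vs 4% (worse) | 15% | 0.0% |
| 4% vs 4% (no effect) | 26% | 0.04% |
| 10% vs 4% (weak effect) | 53% | 2% |
| 40% vs 4% (planned low dose) | 99% | 76% |

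With no effect at 4%, and allowing for the shared placebo group, both doses pass in 14% of trials and at least one in 39%. With 16 per group the figures are 26% for a given dose and 12% for both.

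**Sensitivity.** With equal rates in both groups, a given dose passes in 22% of trials at 2%, 23% at 10%, 22% at 15% and 20% at 20%. At one-sided 0.05 the 4% vs 4% figure rises to 52% (20 per group) or 57% (16 per group).

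**The case against.** The strongest reply is that nothing depends on this test. The primary conclusion rests on Fisher with Simes/Holm, both documents bar a claim without superiority, and no text makes the non-inferiority result a gate or a rescue. The SAP does not say that a pass demonstrates superiority, and readers will have the Fisher p-values and the Newcombe interval. All of that stands, and it limits the severity.

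The 26% is also not a type I error rate. When the two rates are equal the non-inferiority null is false, so 26% is the power of a test doing what it was built to do. At a true boundary, 5% vs 20%, it passes in 1.4% of trials, so it does not exceed its level there. It also fails in most trials of an inert product. This stands too: the fault is in the question asked, not in the calculation.

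Finally, the sponsor may have meant superiority by more than 15 points, or the details may be in separate programming specifications. But the words used are non-inferiority and margin of inferiority. If something else was intended, the bullet is wrong as written and still has to be changed in the SAP.

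**Conclusion.** The concern holds. As written, the test excludes only a deficit of 15 points or more, which is impossible at the planned placebo rate, so a pass is no evidence for the trial's hypothesis. A dose with no effect passes in about a quarter of trials (20% to 26% for placebo rates from 2% to 20%, with 20 per group), nearly always alongside a non-significant Fisher test.

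These sizes assume a margin in percentage points, one-sided 0.025 and the pediatric ITT numbers. One-sided 0.05 would raise the pass rates. The logical point needs only the ordinary direction of a non-inferiority test. The primary inference and its type I error are untouched, so this should be fixed but does not threaten the trial's conclusion.

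**What to change.** Delete the Farrington-Manning bullet from SAP 7.8.1. The Fisher test answers the superiority question, and the Newcombe 95% CI shows what deficit or benefit the data exclude. The cost is one bullet and one output removed, with nothing lost that bears on superiority.

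If the sponsor wants a margin-based analysis, define it as superiority by a margin: state the null hypothesis and its sign, the scale, the one-sided 0.025 level, the population, and a justified margin. The 15 points should not be carried over by default, since neither document justifies it as a superiority threshold. This route requires the margin to be chosen and justified before database lock.
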